3.8.3.4 Withdrawal of Consent/Assent

All subjects have the right to withdraw their consent/assent from further participation in the trial at any time without prejudice. Subjects cannot withdraw consent/assent for use of data already collected as part of the trial, but only for future participation. The investigator can also discontinue a subject’s participation in the trial at any time if medically necessary. Unless the subject provides their written withdrawal of consent/assent or there is other written documentation by the investigator confirming the subject’s verbal intent to completely withdraw from the trial, subjects should be followed for all protocol-specified evaluations and assessments, if possible.

Complete withdrawal of consent/assent requires a subject’s refusal of ALL of the following methods of follow-up (these methods of follow-up will also be noted in the trial ICF):

- Participation in all follow-up procedures specified in the protocol (whether in-clinic, by telephone, or by an in-home visit).
- Participation in a subset of protocol-specified follow-up procedures (by a frequency schedule and method, as agreed by subject and staff).
- Contact of the subject by trial personnel, even if only by telephone, to assess current medical condition, and obtain necessary medical or laboratory reports relevant to the trial’s objectives.
- Contact of alternative person(s) who have been designated in source records as being available to discuss the subject’s medical condition, even if only by telephone, mail, or e-mail (eg, family, spouse, partner, legal representative, friend, neighbor, or physician).
- Access to medical information from alternative sources (eg, hospital/clinic medical records, referring doctor’s notes, public records, dialysis, transplantation or vital registries, social media sources).

Withdrawal of consent/assent is a critical trial event and therefore should be approached with the same degree of importance and care as is used in initially obtaining informed

Protocol 156-12-298

consent. The reasons for a subject's intended withdrawal need to be completely understood, documented, and managed to protect the rights of the subject and the integrity of the trial. A subject may initially express their desire to interrupt or discontinue IMP administration, which is not equivalent to a complete withdrawal of consent/assent for further participation (see [Section 3.8.3.1](#) and [Section 3.8.3.2](#)). A subject may, however, indicate that further trial participation is creating a burden on their work/school or social schedule. Therefore, the investigator should follow the procedures outlined in [Section 3.8.3.3](#) to determine if the subject can continue participation in the trial if modifications to his/her treatment and/or schedule of assessments can be accommodated. Only subjects who withdraw their permission for all of the above degrees of follow-up are considered to have completely withdrawn their consent/assent to participate in the trial.

3.9 Screen Failures

A screen failure subject is one from whom informed consent is obtained and is documented in writing (ie, subject signs an ICF), but who is not randomized or otherwise-assigned treatment (ie, washout or placebo).

For the purposes of this trial, treatment begins with the first dose of IMP. If a subject fails to qualify for the trial during screening, he/she is permitted to be rescreened at a later date. However, a new ICF/IAF must be signed prior to reinitiating screening procedures. Subjects are permitted to be rescreened only once. Rescreened subjects will be assigned a new screening number.

3.10 Definition of Completed Subjects

The treatment period is defined as the time period during which subjects are evaluated for primary and/or secondary objectives of the trial irrespective of whether or not the subject actually consumed all doses of the IMP. Subjects who are evaluated at the last scheduled visit during the treatment period will be defined as trial completers. For purposes of this trial,

- Subjects who are randomized and take IMP through the Month 12 visit in Phase A and complete some or all of the trial visit assessments will be defined as *Phase A on-treatment completers*.
- Subjects who are randomized and discontinue IMP prior to the Month 12 visit in Phase A and complete some or all of the trial visit assessments will be defined as *Phase A off-treatment completers*.

Protocol 156-12-298

- Subjects who take IMP through the Month 24 visit in Phase B and complete some or all of the trial visit assessments will be defined as *On-treatment trial completers*.
- Subjects who discontinue IMP prior to the Month 24 visit in Phase B and complete some or all of the trial visit assessments will be defined as *Off-treatment trial completers*.
- Subjects who are randomized, take IMP but do not complete the Phase A Month 12 visit or the Phase B Month 24 visit will be defined as *Trial non-completers*.

3.11 Definition of Subjects Lost to Follow-up

Subjects who cannot be contacted on or before their last trial visit during the treatment period, who do not have a known reason for discontinuation (eg, withdrew consent or AE), and for whom a survival status at the end of the trial cannot be determined will be classified as “lost to follow-up” as the reason for discontinuation. Vital status can be determined from a variety of sources, either by obtaining acceptable documentation for death (ie, death certificate, medical records, public records, statement by a family member or primary care physician) or acceptable documentation for life (ie, direct contact with the subject, medical records, successful telephone contact with the subject, statement by a family member or primary care physician, or public records).

The site will make 3 documented attempts to contact the subject by telephone and in the event the site is unable to reach the subject by telephone, the site will attempt to contact the subject via certified mail or an alternative similar method, where appropriate, before assigning a “lost to follow-up” status.

3.12 Subject Compliance

The date and time of the first dose of IMP administration will be recorded in source documentation and the eCRF. The date and time of each dose administered in the clinic will also be recorded. Information regarding any missed or inappropriately administered doses will also be documented in source documentation and the eCRF.

Accountability and compliance verification should be documented in the subject’s trial records. Subjects must be counseled on the importance of taking the IMP as directed at all trial visits and work with their physicians around planned interruptions. If poor compliance continues (eg, multiple missed doses resulting in < 80% overall compliance at any point in the trial), discontinuation from the trial should be considered. This decision will be documented by the investigator in consultation with the medical monitor.

Protocol 156-12-298

3.13 Protocol Deviations

In the event of a significant deviation from the protocol due to an emergency, accident, or mistake (eg, violation of informed consent process, IMP dispensing or subject dosing error, treatment assignment error, subject enrolled in violation of eligibility criteria or concomitant medication criteria), the investigator or designee will contact the sponsor at the earliest possible time by telephone. The investigator and sponsor or designee will come as quickly as possible to a joint decision regarding the subject's continuation in the trial. This decision will be documented by the investigator and the sponsor or designee, and reviewed by the site monitor.

4 Restrictions

4.1 Prohibited Medications

Medications or surgical therapies used for the purpose or potential for modifying the progression of PKD cyst growth or development will be prohibited. These include, but are not restricted to, somatostatin agonists, rapamune (sirolimus), anti-sense ribonucleic acid (RNA) therapies, tolvaptan, and other vasopressin antagonists eg, OPC-31260 (mozavaptan), Vaprisol (conivaptan), or agonists (eg, desmopressin). If a subject develops a medical need for cyst reduction therapy, during trial participation, this will be addressed with the appropriate physician. The subject would then be discontinued from treatment at the time of surgical intervention. The subject will remain in the trial and may restart treatment 6 weeks after surgical intervention at the discretion of the investigator.

Continuous or short-term use of other medications, while not prohibited, may be restricted by the investigator because of their potential for interference with metabolism or efficacy endpoints. This includes the use of diuretics which may be used intermittently, but not within 7 days of a urine assessment. Diuretics are not generally recommended in ADPKD due to their tendency to increase AVP levels through relative dehydration or volume depletion; thus, chronic use of diuretics (eg, for hypertension) will be prohibited due to potential endpoint interference and is an exclusionary criterion for this trial. Subjects taking such agents must first sign an ICF and then agree to be switched to an alternate form of therapy in order to be eligible for the trial. Subjects must be on a stable dose of their antihypertensive medications at randomization.

Some drugs are known to alter creatinine concentrations so, while not prohibited, subjects should alert their trial doctor, and any other healthcare providers, to take this into consideration when considering changes in their prescribed or over-the-counter

Protocol 156-12-298

medications. A brief list would include: cimetidine, nonsteroidal antiinflammatory drug medications like aspirin or ibuprofen, chemotherapy drugs, and cephalosporin.

Since tolvaptan is a sensitive CYP3A4 substrate, CYP3A4 inhibitors should be avoided during the trial, with the exception of amiodarone, which was found to have no effect on tolvaptan concentrations. CYP3A4 inducers should also be avoided. If these drugs are to be used, the medical monitor should be contacted and IMP administration must be interrupted (see [Section 3.8.3.1](#)). A partial list of CYP3A4 inhibitors can be found in [Table 4.1-1](#).

Table 4.1-1 CYP3A4 Inhibitors (Partial List)			
boceprevir	clarithromycin	clotrimazole (if used orally)	indinavir
itraconazole	ketoconazole (if used orally)	lopinavir	mibefradil
nefazadone	nelfinavir	posaconazole	ritonavir
saquinavir	telaprevir	telithromycin	voriconazole

4.2 Dietary Restrictions and Recommendations

Fluid intake is generally encouraged in subjects with PKD. Given the potential for dehydration with tolvaptan treatment, all subjects should be instructed to ingest water or noncaloric fluids in anticipation of, or at the first sign of thirst in order to avoid excessive thirst or dehydration. Upon consent, all subjects should receive the recommendation to ingestion of at least 1.5 to 2 liters of fluid (including in solid, semi-solid, and liquid foods) per day. This recommendation should start during screening and continue through the end of the trial. Additionally, subjects should ingest 1 to 2 cups of water before bedtime regardless of perceived thirst and replenish fluids overnight with each episode of nocturia. Dehydration will be monitored by subject self-assessment of changes in body weight and reporting of symptoms. Acute changes of > 3% of body weight (increase or decrease) over any 7-day period should be noted. Subjects should be instructed to report acute changes in body weight to the trial physician for further evaluation and recommendations.

Subjects should be advised that the ingestion of pomelo, grapefruit, or Seville orange juice or other products would be expected to increase tolvaptan concentrations and these should not be consumed during trial participation.

Protocol 156-12-298

5 Reporting of Adverse Events

5.1 Definitions

An AE is defined as any untoward medical occurrence in a patient or clinical trial subject administered a medicinal product and which does not necessarily have a causal relationship with this treatment. AEs would not include information recorded as medical history at screening for pre-planned procedures for which the underlying condition was known and no worsening occurred. An adverse reaction is any untoward and unintended response to an IMP related to any dose administered.

A suspected adverse reaction is any AE for which there is a reasonable possibility that the IMP caused the AE. For the purpose of Investigational New Drug (IND) safety reporting, “reasonable possibility” means there is evidence to suggest a causal relationship between the IMP and the AE. Suspected adverse reaction implies a lesser degree of certainty about causality.

An SAE includes any event that results in any of the following outcomes:

- Death.
- Life-threatening; ie, the subject was, in the opinion of the investigator, at immediate risk of death from the event as it occurred. It does not include an event that, had it occurred in a more severe form, might have caused death.
- Persistent or significant incapacity/disability or substantial disruption of the ability to conduct normal life functions.
- Requires in-patient hospitalization or prolongs hospitalization.
 - Hospitalization itself should not be reported as an SAE; whenever possible the reason for the hospitalization should be reported.
 - Hospitalizations or prolonged hospitalizations for social admissions (ie, those required for reasons of convenience or other non-medical need) are not considered SAEs.
- Congenital anomaly/birth defect.
- Other medically significant events that, based upon appropriate medical judgment, may jeopardize the subject and may require medical or surgical intervention to prevent one of the outcomes listed above; eg, allergic bronchospasm requiring intensive treatment in an emergency room or home, blood dyscrasias or convulsions that do not result in hospitalization, or the development of drug dependency or drug abuse.

Nonserious Adverse Events are all AEs that do not meet the criteria for a “serious” AE.

Immediately Reportable Event (IRE):

- Any SAE.

Protocol 156-12-298

- Any AE related to occupational exposure.
- Potential DILI case (see [Section 5.4.1](#)) and any new liver abnormality requiring the liver eCRF completion.
- Any subject reporting an AE of special interest (eg, skin neoplasms or glaucoma)
- Pregnancies are also defined as IREs. Although normal pregnancy is not an AE, it will mandate IMP discontinuation and must be reported on an IRE form to the sponsor. Pregnancy will only be documented on the AE eCRF page if there is an abnormality or complication.
- Additionally, in the European Union, events involving overdose, misuse, and abuse as well as reported lack of efficacy must also be reported as IREs.

Clinical Laboratory Test Value Changes: It is the investigator's responsibility to review the results of all laboratory tests as they become available. This review will be documented by the investigator in source documents. For each abnormal laboratory test result, the investigator needs to ascertain if this is an abnormal (ie, clinically significant) change from baseline for that individual subject. This determination, however, does not necessarily need to be made the first time an abnormal value is observed. The investigator may repeat the laboratory test or request additional tests to verify the results of the original laboratory tests. If this laboratory value is considered medically relevant by the investigator (subject is symptomatic, requiring corrective treatment or further evaluation), or if the laboratory value leads to discontinuation, and/or fulfills a seriousness criterion, this is considered an AE.

Severity: Adverse events will be graded on a 3-point scale and reported as indicated on the eCRF. The intensity of an adverse experience is defined as follows:

1 = Mild: Discomfort noticed, but no disruption to daily activity.

2 = Moderate: Discomfort sufficient to reduce or affect normal daily activity.

3 = Severe: Inability to work or perform normal daily activity.

IMP Causality: Assessment of causal relationship of an AE to the use of the IMP is defined as follows:

Related: There is a reasonable possibility of a temporal and causal relationship between the IMP and the AE.

Not Related: There is no temporal or causal relationship between the IMP and the AE.

Protocol 156-12-298

5.2 Eliciting and Reporting Adverse Events

The investigator will periodically assess subjects for the occurrence of AEs. To avoid bias in eliciting AEs, subjects should be asked the nonleading question: "How have you felt since your last visit?" All AEs (serious and nonserious) reported by the subject must be recorded on the source documents and eCRFs provided by the sponsor. AE collection (serious and nonserious) is to begin after a subject has signed the ICF.

Use medical terminology in AE reporting. Adverse events should be reported as a single unifying diagnosis whenever possible or, in the absence of a unifying diagnosis, as individual signs or symptoms. Exacerbation or disease progression should be reported as an AE only if there are unusual or severe clinical features that were not present, or experienced earlier, or not expected based on the course of the condition.

In addition, the sponsor must be notified immediately by telephone, fax, or e-mail of any IREs according to the procedure outlined below, in [Section 5.3](#). Special attention should be paid to recording hospitalization and concomitant medications.

5.3 Immediately Reportable Events

The investigator must immediately (ie, within 24 hours) report after either the investigator or site personnel become aware of any IREs as defined in [Section 5.1](#) by telephone, fax, or e-mail to the sponsor using the contact information on the cover page of this protocol. An IRE form must be completed and sent by e-mail, fax, or overnight courier to the sponsor. (Please note that the IRE form is NOT the AE eCRF page.)

Subjects experiencing IREs should be followed clinically until their health has returned to baseline status or until all parameters have returned to normal or have otherwise been explained. It is expected that the investigator will provide or arrange appropriate supportive care for the subject and will provide prompt updates on the subject's status to the sponsor.

5.4 Assessment of Liver Symptoms, Signs or Test Abnormalities

5.4.1 Potential Drug-Induced Liver Injury

For a subject who experiences an elevation in AST or ALT that is ≥ 3 times the upper limit of normal (ULN), BT and ALP should also be evaluated. If significant abnormalities in transaminases and/or bilirubin are confirmed, other testing to fully evaluate the likely proximate cause should be undertaken with the option of consulting with local hepatic experts for interpretation and guidance. All results should be made available to the sponsor and the HAC.

Protocol 156-12-298

If BT is \geq 2 times the ULN, complete an IRE form with all values listed and also report as an AE on the CRF.

Testing for hepatic transaminase (ALT/AST), ALP, and BT will be performed during screening/baseline and at each monthly visit. Management of liver abnormalities is discussed in the paragraphs below.

5.4.2 Requirements for Repeated Liver Testing

5.4.2.1 Liver Transaminase Elevations

Management of abnormal liver function test results should be based on the investigator's clinical judgment. The appearance of any suspicious symptom or sign should trigger prompt testing of hepatic function (ie, within 48 to 72 hours). A liver function test result that is $2 \times$ ULN is generally accepted as a clinically significant occurrence across various medical disciplines.

For a subject who experiences an elevation in AST or ALT that is $\geq 2 \times$ ULN or whose levels increase \geq 2 times their initial baseline value in subjects with an elevated baseline value, a BT level should also be evaluated. Elevated values should be confirmed via retest within 48 to 72 hours.

5.4.2.2 Guidelines for Repeat Liver Testing in Subjects with Normal Values at Screening

The appearance of any suspicious symptom or sign should trigger prompt testing of hepatic function (ie, within 48 to 72 hours). Local laboratory testing is acceptable, ideally with a concurrent central laboratory sample for confirmation.

Any transaminase or bilirubin values which exceed $2 \times$ ULN should also prompt immediate retesting within 48 to 72 hours. While values remain in an abnormal range, testing frequency should be increased to at least weekly for the first month, gradually returning to monthly as indicated by the results.

If hepatic injury is suspected, tolvaptan should be promptly discontinued, appropriate treatment should be instituted, and investigations should be performed to determine probable cause. Such an event should be reported and followed until resolution.

5.4.2.3 Subjects with Elevated Liver Transaminase at Screening

Subjects found to have liver laboratory abnormalities at screening or who have a history of non-ADPKD-related liver disease will require further evaluation. These subjects will need to have the special liver eCRF (see [Section 5.4.5](#)) completed and additional testing

Protocol 156-12-298

will be required during screening to confirm the stability of the abnormality prior to randomization to confirm eligibility. Management of such subjects should be closely coordinated with the trial's medical monitor. In these subjects, further changes in liver test levels of $> 2 \times$ upper limit of their highest screening value at any point postscreening should prompt re-testing within 48 to 72 hours. Should such an increase occur during treatment with IMP, the subject will be immediately discontinued from treatment. IMP should not be resumed until monitoring indicates abnormalities have resolved, are stable or are not rapidly increasing, and then only with an increased frequency of monitoring.

Protocol 156-12-298

5.4.3 Guidelines for Repeat Testing of Liver Transaminases

The following guideline for repeat testing may be used by investigators as a reference for any subject with an ALT or AST $\geq 2 \times$ ULN:

- ALT, AST, ALP, and BT should be repeated within 48 to 72 hours (needed to confirm abnormalities and determine if they are increasing or decreasing).
- Inquiries should be made about symptoms (fatigue, nausea, vomiting, right upper quadrant pain or tenderness, fever, and/or rash) and signs like jaundice or yellowish discoloration of sclera.
- Close observation is required if symptoms persist or repeat testing shows ALT or AST $\geq 3 \times$ ULN for subjects with normal baseline measures OR 2-fold increases above baseline values for subjects with elevated values before drug exposure. If close monitoring is not possible, the drug should be interrupted until such monitoring is possible or the drug should be permanently discontinued.
- All trial subjects with evidence of possible DILI should be followed until all abnormalities return to normal or to the baseline state.

Close observation may involve:

- Repeating liver enzymes and serum bilirubin tests 2 or 3 times weekly.
- Frequency of retesting can decrease to once a week or less if abnormalities stabilize or if the trial drug has been interrupted/discontinued and the subject is asymptomatic.
- Obtaining a more detailed history of symptoms and prior or concurrent diseases.
- Obtaining a history of concomitant drug use (including nonprescription medications and herbal and dietary supplement preparations), alcohol use, recreational drug use, special diets, and change in diet.
- Ruling out acute viral hepatitis types A, B, C, D, and E; autoimmune or alcoholic hepatitis, nonalcoholic steatohepatitis; hypoxic/ischemic hepatopathy, and biliary tract disease.
- Obtaining a history of exposure to environmental chemical agents.
- Obtaining additional tests to evaluate liver function, as appropriate (eg, international normalized ratio [INR], direct bilirubin).
- Considering gastroenterology or hepatology consultations.

5.4.4 Liver Test Abnormalities and Interruption/Discontinuation of Investigational Medicinal Product

Liver transaminase or bilirubin levels reaching or exceeding $2 \times$ ULN that have an uncertain or rapidly increasing trajectory should prompt at least temporary IMP interruption. IMP should not be resumed until monitoring indicates abnormalities have resolved, are stable or are not rapidly increasing, and then only with an increased frequency of monitoring.

Protocol 156-12-298

A subject must be discontinued from the trial on confirmation of any of the following criteria:

- ALT or AST $\geq 8 \times$ ULN
- ALT or AST $\geq 5 \times$ ULN for more than 2 weeks
- ALT or AST $\geq 3 \times$ ULN and (BT $\geq 2 \times$ ULN or INR > 1.5)
- ALT or AST $\geq 3 \times$ ULN with appearance of fatigue, nausea, vomiting, right upper quadrant pain or tenderness, fever, rash, and/or eosinophilia ($> 5\%$) and signs of jaundice

If an investigator has any question about how to proceed with a particular subject's case, he/she should contact the regional medical monitor to discuss. The United States Food and Drug Administration (US FDA) has issued a guidance for industry regarding this topic. The sponsor is integrating many of the recommendations in this guidance into all of its clinical research programs. Links to this guidance and information from the FDA regarding DILI are provided in the references.^{14,15}

5.4.5 Requirements for Special Reporting Using the Liver Disease Electronic Case Report Form and Immediately Reportable Event Form

The purpose of the liver disease eCRF and optional additional testing is to facilitate review of each subject who presents with, or develops, a liver abnormality during the trial or and to determine the probable cause(s) of these abnormalities. The review will be performed by a blinded, independent, hepatic, adjudication committee using Drug Induced Liver Injury Network (DILIN) probability criteria.¹⁶

- $< 25\%$ = unlikely
- 25% to 50% = possibly
- 51% to 75% = probably
- 76% to 95% = very likely
- $>95\%$ = definite

The result of these analyses may be presented separately from the CSR.

The investigator must complete a special liver disease eCRF and IRE for any subject who:

- 1) Discontinues treatment due to a liver-related AE,
- 2) Reports a serious liver-related AE,
- 3) With normal screening levels develops ALT or AST levels $\geq 3 \times$ ULN,
- 4) With normal screening levels develops BT levels $\geq 2 \times$ ULN, or

Protocol 156-12-298

- 5) With an abnormal screening liver test level develops abnormalities in that test that are $> 2 \times$ the upper limit of their highest screening value.

All subjects meeting any 1 of the above criteria will also be asked to provide an additional set of blood and urine biomarker samples at the time of the event. Additional clinical testing (such as testing for hepatitis serology) may also be indicated and their results reported according to local guidelines.

The liver eCRF and IRE form (see [Section 5.3](#)) should be updated as new information becomes available.

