3.8.3 Individual Subject Discontinuation

3.8.3.1 Treatment Interruption

In this 3-year trial, it is expected that subjects may have 1 or more treatment interruptions during the double-blind, randomized treatment period (Phase A) or the open-label treatment period (Phase B). If a subject's IMP treatment must be interrupted for medical or surgical reasons; liver test abnormalities; use of a prohibited concomitant medication; or other reasons (eg, hospital admission for an invasive procedure, a major medical condition, surgery, dental work, or a temporary situation that prevents subject compliance with the IMP administration schedule), the medical monitor should be consulted.

Scheduled treatment interruption is discouraged during the first month of treatment in Phase A and within 30 days of any scheduled MRI and/or ultrasound assessment. The medical monitor should be contacted if IMP interruption is needed during these time points.

If a subject develops a medical need for cyst reduction therapy, during trial participation, this will be addressed with the appropriate physician. The subject would then be discontinued from treatment at the time of surgical intervention. The subject will remain in the trial and may restart treatment 6 weeks after surgical intervention at the discretion of the investigator.

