3.8.3.3 Documenting Reasons for Treatment Interruption/Discontinuation

A subject may temporarily interrupt or discontinue IMP for a number of reasons including those listed below:

- Reasons related to AE:
 - Subject could not tolerate IMP due to an AE that is annoying or uncomfortable but not serious or hazardous
 - Physician determined that there are potential IMP related safety concern or serious AE (SAE) placing subject at undue hazard
 - SAE
 - Progression of disease leading to dialysis, transplantation, or eGFR decline as determined by the investigator
 - Liver test abnormalities meeting criteria for permanent discontinuation (see [Section 5.4.2.3](#))
 - Clinical signs of DILI (eg, jaundice, right upper quadrant pain)
- Death
- Reasons unrelated to medical condition
- Withdrawal of informed consent (partial related to IMP or complete written withdrawal of consent form)

Protocol 156-12-298

- Lost to follow-up (detailed procedures to prevent subjects from becoming “lost to follow-up” will be provided in the operations manual. These procedures must be followed by the investigator, their staff, or other designated trial personnel)
- Pregnancy (see [Section 5.5](#))
- Termination of all or part of the trial by the sponsor

If the subject temporarily interrupts or discontinues IMP due to an AE, the investigator or other trial personnel, will make every effort to follow the event until it has resolved or stabilized.

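### Protocol 5.4.4 takes subjects with confirmed liver criteria out of the trial, which conflicts with the protocol's own follow-up after an IMP stop

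*Protocol*

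**What the plan says.** Protocol 5.4.4 is headed "Liver Test Abnormalities and Interruption/Discontinuation of Investigational Medicinal Product". Its first paragraph deals with transaminase or bilirubin values at or above 2 × ULN on an uncertain or rising course, which "should prompt at least temporary IMP interruption". It then sets the rule at issue: "A subject must be discontinued from the trial on confirmation of any of the following criteria". The four criteria are:

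- ALT or AST ≥ 8 × ULN
- ALT or AST ≥ 5 × ULN for more than 2 weeks
- ALT or AST ≥ 3 × ULN with BT ≥ 2 × ULN or INR > 1.5
- ALT or AST ≥ 3 × ULN with listed symptoms and signs of jaundice

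The reporting rules in 5.4.5 cover, among others, a subject who "Discontinues treatment due to a liver-related AE".

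Elsewhere the protocol separates stopping IMP from leaving the trial. Under 3.8.3.2 and Table 3.7-2 footnote c, a subject who stops IMP in Phase B has a 7-day safety visit and is then followed every 6 months through Phase B. Sections 3.7.2.1 and 3.7.2.2 keep TKV imaging at the scheduled times for subjects off IMP. Section 3.8.3.4 makes follow-up the default unless complete withdrawal is documented, and lets the investigator end participation when medically necessary. In 3.8.3.1 a subject having cyst surgery stops treatment, yet "The subject will remain in the trial and may restart treatment 6 weeks after surgical intervention".

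Section 3.8.3.3 opens with "A subject may temporarily interrupt or discontinue IMP for a number of reasons including those listed below" and lists "Liver test abnormalities meeting criteria for permanent discontinuation", with a reference to 5.4.2.3.

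**The concern.** A site with a confirmed case has two instructions. One sends the subject out of the trial. The other stops the drug and keeps the subject on six-monthly visits. The wording in 5.4.4 is mandatory, so a site that follows it to the letter is not departing from the protocol.

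This matters because of how missing data are handled. Protocol 7.3 and SAP 5.2 summarize observed values only, and their one stated mitigation is to encourage subjects who stop treatment to come back for their remaining visits. A literal 5.4.4 switches that mitigation off for a group defined by liver response. The primary objective is long-term safety in children and adolescents, where growth, pubertal stage and renal function after the drug is stopped are of interest.

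**Working it through.** This is a comparison of texts, followed by a count of what a literal reading would lose. The plan gives no figure of its own to reproduce.

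**Step 1: which texts conflict.** Section 5.4.4 ends trial participation. Section 3.8.3.2, Table 3.7-2 footnote c and the 3.8.3.4 default continue it after an IMP stop. One subject cannot follow both. The heading of 5.4.4, its first paragraph and 5.4.5 suggest that an IMP stop was meant, but they do not exclude trial exit, because leaving the trial also means stopping IMP.

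**Step 2: the cross-reference.** Section 3.8.3.3 speaks of permanent-discontinuation criteria and points to 5.4.2.3. That section concerns subjects with abnormal liver tests at screening. It says "Should such an increase occur during treatment with IMP, the subject will be immediately discontinued from treatment" and then sets conditions for resuming IMP, so it contains no permanent criteria. The mandatory, confirmed thresholds are in 5.4.4, which is the evident target.

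**Step 3: what a literal reading leaves in place.**
- AEs are collected to 14 days after the last dose (5.7), whether or not the subject stays in follow-up.
- Possible drug-induced liver injury is followed until values return to normal or baseline (5.4.3).
- The EoTx visit (3.8.3.2) and the 7-day visit (3.7.1.4.1) still take place. The EoTx column of Table 3.7-2 includes vital signs, height and weight, chemistry, creatinine, LFTs and Tanner stage.

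**Step 4: what it removes, in Phase B.** Inputs from Table 3.7-2: six-monthly visits at Months 6, 12, 18 and 24 (4 visits), and TKV scans at Months 12 and 24 (2 scans). Loss = scheduled items falling after removal.

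| Removed | Visits lost | Scans lost |
|---|---|---|
| Before Month 6 | 4 of 4 | 2 of 2 |
| Months 6 to 12 | 3 of 4 | 2 of 2 |
| Months 12 to 18 | 2 of 4 | 1 of 2 |
| Months 18 to 24 | 1 of 4 | 1 of 2 |

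These are calendar counts. The EoTx visit supplies one off-schedule set of measurements in each row. Tanner loss is smaller for a subject already at Stage 5. Section 3.7.1.2.6 lists a scan at Month 24 or end of treatment, while footnote f of the table requires none at EoTx. Either way, an early EoTx scan would in general not be a Month 12 or Month 24 value.

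**Step 5: the weight of one subject.** Assume 60 to 100 randomized 1:1 and all entering Phase B. One subject is then 1/100 = 1.0% to 1/60 = 1.7% of the pooled set, and 1/50 = 2.0% to 1/30 = 3.3% of a prior-arm column; both shares rise if fewer enter. The documents give no rate for meeting the criteria, so no expected number of subjects follows.

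**The case against.** The strongest reply is that this is a wording slip which the protocol largely resolves. Section 3.8.3.4 counts a subject as completely withdrawn only when every method of follow-up is refused, and 5.4.4 tells investigators to take questions to the medical monitor. That makes the IMP-stop reading the more natural one. But neither passage overrides a mandatory sentence, and case-by-case advice can differ between sites.

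Three points of the reply stand and limit the claim.

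- A reader might infer that the 5.4.4 heading, 5.4.5 and the 3.8.3.3 list themselves contradict trial exit. They do not. The 3.8.3.3 list includes pregnancy, and 5.5 both stops IMP and withdraws the pregnant subject from the trial.
- A reader might infer that liver safety data would be lost. Step 3 shows otherwise: AE collection, injury follow-up and the EoTx visit remain. What is lost is off-drug data, which bear less directly on the safety of treatment. Scan collection in Phase B was also relaxed by the COVID-19 addendum.
- A reader might infer that liver-led stops would go uncounted, because SAP 6.1 tabulates only trial discontinuations. Under 5.1 a laboratory value that leads to discontinuation is an AE, so a liver-led stop reaches SAP 9.2 and Protocol 7.9.1. What SAP 6.1 leaves out is IMP stops for other reasons, which is a separate reporting matter.

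**Conclusion.** The inconsistency is real and should be corrected. Section 5.4.4 mandates trial exit where 3.8.3.2, Table 3.7-2 footnote c and 3.8.3.4 call for continued follow-up, and the 3.8.3.3 pointer leads to the wrong section.

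The consequence is limited to Phase B off-drug laboratory and eGFR, growth, Tanner and TKV data: one to four visits and one or two scans per affected subject, and only where a site applies the sentence literally. The visit count assumes that follow-up after an IMP stop uses the Month 6, 12, 18 and 24 visits. The number affected could be zero.

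A reader might take this as bias in a treatment comparison. The documents do not support that. Phase B is open-label and descriptive, and Amendment 2 states that all Phase A assessments were complete. The issue is completeness of long-term data in a liver-selected group; the size and direction of any bias cannot be derived.

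**What to change.** In Protocol 5.4.4, replace *from the trial* with *permanently from IMP, with follow-up per 3.8.3.2*. Keep the four thresholds as they are, and keep the investigator's power under 3.8.3.4 to end participation when medically necessary. In 3.8.3.3, change the reference from 5.4.2.3 to 5.4.4.

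The cost is a short protocol amendment under Section 13, with IRB/IEC submission as local rules require, across approximately 20 centers. The visits are already in the schedule and IMP discontinuation is already recorded on the eCRF, so no new visit or data item is needed. No Phase A edit is needed.

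Optional and separate: a table in SAP 6.1 of IMP discontinuation for all reasons alongside trial discontinuation, using the completer categories of Protocol 3.10. Aligning the discretionary wording in 3.12, and repeating the allowance for off-IMP scans in 3.7.1.2.4 and 3.7.1.2.6, would be editorial only.
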